U NOVARTIS

Clinical Development

AIN457A

CAIN457AIT01 / NCT02394561

A 24-week, multicenter, proSpective stUdy to evaluate the PASI 90 clinical response rate and the safety PRofile of sEcukinuMab 300 mg in Cw6-negativE and Cw6-positive patients with moderate to severe chronic plaque-type psoriasis (SUPREME) – amended with an extension treatment period of up to 48 weeks

Statistical Analysis Plan (SAP)

Author:

Document type: SAP Documentation

Document status: Final version Amendment 2.0

Release date: 20-Sep-2017

Number of pages: 55

Property of Novartis For business use only May not be used, divulged, published or otherwise disclosed without the consent of Novartis

Document History – Changes compared to previous final version of SAP

Date	Time point	Reason for update	Outcome for update	Section and title impacted (Current)
09-Jun-2016	Prior to DB lock	1 st draft version		
04-Jul-2016			Updated as per comments	
04-Aug-2016			Updated as per comments	
17-Sep-2016				
24-Oct-2016		Final version		
16-Jan-2017		Amendment 1.0	Visit Window approach added. DLQI and HADS scoring method added.	Section 2
27-Apr-2017			Added MMRM analysis with MI approach Added Non-responder analysis	

20-Sep-2017	Amendment 2.0	Summaries and analyses are extended based on 72 weeks duration.	General:
		Analysis Sets added for clarity or additional analyses:	Section 2.2 Analysis sets
		 All patients: all patients who signed informed consent and entered in the study, including screen failure. 	
		• Core phase completers set: All patients who completed the Core phase visits (Week 24) are called core phase completer set.	
		Analysis Sets updated/ clarified (in bold):	
		 Safety: all enrolled patients included in the FAS population who were given at least one dose of study drug. 	Section 2.3.1:
		 Intent-to-treat (ITT): all patients included in the safety population with at least one post-baseline efficacy assessment and with the Cw6 assessement. 	
		By visit disposition summary table is added.	
		P-values of comparison of cohorts will be analysed based on stratified CMH, and logistic model with covariates (for categorical variables) and ANCOVA (for continuous variables).	Section 2.3.2:
		Total number of comorbidities (all medical histories) between cohorts will be analyzed by Poisson model adjusted by covariates	Section 2.4.2:

		5.1.2	Concomitant medication date imputation	
	5.2	AEs co	ding/grading	
	5.3	Labora	tory parameters derivations	
	5.4	Statistic	cal models	
		5.4.1	Primary analysis	
		5.4.2	Key secondary analysis	
		5.4.3	Secondary analysis	
	5.5	Rule of	f exclusion criteria of analysis sets	53
6	Refe	ence		

List of abbreviations

ADR	Adverse Drug Reaction		
AE	Adverse Event		
ALT	Alanine Aminotransferase		
ALP	Alkaline Phosphatase		
AST	Aspartate Aminotransferase		
ATC	Anatomical Therapeutic Chemical		
BMI	Body Mass Index		
BUN	Blood Urea Nitrogen		
CASPAR	Classification Criteria for Psoriatic Arthritis		
CRF	Case Report Form		
CTCAE	Common Terminology Criteria for Adverse Events		
CSR	Clinical Study report		
DAR	Dose Administration Record		
DLQI	Dermatology Life Quality Index		
EC	Ethics Committee		
eCRF	Electronic Case Report Form		
EDC	Electronic Data Capture		
EMA	European Medicines Agency		
FAS	Full Analysis Set		
GGT	Gamma Glutamyl Transpeptidase		
GCP	Good Clinical Practice		
HADS	Hospital Anxiety and Depression Scale		
HBV	Hepatitis B Virus		
HCV	Hepatitis C Virus		
HIV	Human Immunodeficiency Virus		
HLA	Human Leukocyte Antigen		
hs-CRP	High Sensitivity C Reactive Protein		
IB	Investigator's Brochure		
ICH	International Conference on Harmonization		
IL	Interleukin		
ITT	Intent-to-treat		
LDH	Lactate Dehydrogenase		
LFT	Liver Function test		
LOCF	Last Observation Carried Forward		
MedDRA	Medical Dictionary for Drug Regulatory Affairs		
PASI	Psoriasis Area Severity Index		
PP	Per-Protocol		
PPD	Purified Protein Derivative		
PPS	Per-Protocol Set		
PRO	Patient-reported Outcomes		

PUVA	Psoralen combined with Ultraviolet A		
QoL	Quality of Life		
SAE	Serious Adverse Event		
S.C.	Subcutaneous		
SD	Standard Deviation		
SNP	Single Nucleotide Polymorphism		
SUSAR	Suspected Unexpected Adverse Reaction		
TNF	Tumor Necrosis Factor		
TFLs	Tables, Figures, Listings		
ULN	Upper Limit of Normal		
WHO	World Health Organization		

1 Introduction

This document contains details of the statistical methods which will be used in the phase IIIb clinical trial CAIN457AIT01. This document gives detailed statistical methodology used in the analysis of this study. This is a multicenter, prospective study involving Cw6-negative and Cw6-positive patients affected by moderate to severe chronic plaque psoriasis.

The study has four periods: a screening period consisting of two visits (pre-screening and screening), an induction period of 4 weeks, a maintenance period of 20 weeks and an extension period of 48 weeks.

This SAP will be used for the analysis of both Core phase and Extension phase.

Data will be analyzed by statistical software SAS version 9.2 or later according to the data analysis Section 9 of the study protocol which is available in Appendix 16.1.1 of the CSR. Important information is given in the following sections and details are provided, as applicable, in Appendix 16.1.9 of the CSR.

1.1 Study design

This is a multicenter, prospective study involving Cw6-negative and Cw6-positive patients affected by moderate to severe chronic plaque psoriasis.

The study has four periods: a screening period consisting of two visits (pre-screening and screening), an induction period of 4 weeks, a maintenance period of 20 weeks and an extension period of 48 weeks. The schematic of study design is given in Figure 1.1-1 (for Core phase) and in Figure 1.1-2 (for Extension phase) below.

At pre-screening (day -28), patients will be centrally assessed for Cw6 positivity or negativity and stratified into two cohorts (Cw6-negative and Cw6-positive patients). Both patients and investigators will be blinded to the results with respect to Cw6. At the same time 308-TNF α polymorphism will be centrally determined.

After a full screening visit, each eligible patient will be treated according to an induction regimen of two injections of secukinumab 150 mg a week for five weeks starting at baseline (week 0), followed by a maintenance period of one treatment (two injections) per month. At week 16, patients achieving a PASI 50 response will be eligible to continue on secukinumab for an additional 8 weeks. After a total of 24 weeks, willing patients reaching at least a PASI 75 response will enter an extension treatment period of up to 48 weeks. The total duration of the study, including the extension period, is therefore of 72 weeks. For all summaries of "by phases" analyses, total number of patients (N) for extension phase will be the number of patients who have entered the extension. All percentages in extension phase will be based on this N.

Primary analysis time point

The primary analysis will be performed at 16 weeks, and thereafter for up to 72 weeks.

Planned number of patients

The study plans to enroll about 406 adult men or women, of which 365 are evaluable patients, diagnosed with moderate to severe chronic plaque psoriasis for at least 6 months. The patients must be candidates for systemic therapy and may be treatment naïve or have failed to respond to other systemic therapy (including cyclosporine, methotrexate, psoralen combined with ultraviolet A (PUVA) or to an anti-TNFa (or is intolerant and/or has a contraindication to these). The study plans to involve approximately 50 centers. The extension phase will include approximately 306 of the patients initially enrolled in the core study.

Interim analyses

Novartis

No interim analysis will be performed for this study.

Figure 1.1-1: Study Design for Core Phase

Figure 1.1-2: Study Design for Extension Phase

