4.3 Eligibility criteria for entering the extension treatment period

1. Patients who have completed the CAIN457AIT01 core study.
2. Written informed consent for protocol amendment 2 must be obtained before patients proceed to the extension treatment period.
3. Patients must be deemed to be benefiting from the study drug based on at least a PASI 75 response rate after 24 weeks of treatment.

5 Treatment

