5.5.9 Discontinuation of study treatment and premature patient withdrawal

Patients may voluntarily withdraw from the study for any reason at any time. They may be considered withdrawn if they state an intention to withdraw, fail to return for visits, or become lost to follow-up for any other reason.

If premature withdrawal occurs for any reason, the investigator must make every effort to determine the primary reason for a patient's premature withdrawal from the study and record this information.

The investigator should discontinue the investigational treatment for a given patient and/or withdraw the patient from the study if, on balance, he/she believes that continuation would be detrimental to the patient's well-being.

The investigational treatment must be discontinued under the following circumstances:

- Withdrawal of informed consent
- Severe adverse events that, in the opinion of the Investigator, warrant discontinuation
- Pregnancy
- Use of prohibited treatment as per [Table 5-1](#)
- Any other protocol deviation that results in a significant risk to the patient's safety

Patients that do not achieve PASI 50 at week 16 will terminate treatment. For patients who are lost to follow-up (i.e. those patients whose status is unclear because they fail to appear for study visits without stating an intention to withdraw), the investigator should show "due diligence" by documenting the steps taken to contact the patient, e.g. dates of telephone calls, registered letters in the source, etc.

Patients who are prematurely withdrawn from the study will not be replaced by an equal number of newly enrolled patients.

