• For the subjects who did not enter Extension Phase, all events/medications belongs to Core Phase

- · If event/medications start date is on or before visit date of E0, then APERIOD=Core Phase
- If event/medications start date is after visit date of E0, then APERIOD=Extension Phase.

For Planned data (i.e., Visit wise, all safety and efficacy) will be derived as below:

- · Visits before E0 will belong to Core Phase
- · Visits on or after E0 will belong to Extension Phase

Basically reporting will be done for visit assessment data in extension phase which is collected on or after ICF is signed for extension phase.

The above rules are irrespective of whether V12 visit date and E0 visit date are same or different.

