2.2 Analysis sets

The following analysis populations will be defined for statistical analysis.

- All patients: all patients who signed informed consent and entered in the study, including screen failure.
- Full Analysis Set (FAS): all enrolled patients (i.e. patients entered at week 0 visit 3).
- Safety: all enrolled patients included in the FAS population who were given at least one dose of study drug.
- Intent-to-treat (ITT): all patients included in the safety population with at least one post-baseline efficacy assessment and with the Cw6 assessment.
- Per-Protocol (PP): all patients included in the ITT population who completed the study without any major protocol violation.
- Core phase completers set: All patients who completed the Core phase visits (Week 24) are called core phase completer set.

The primary and secondary objectives will be evaluated on the ITT population. A supportive analysis will be done on the PP population.

All safety evaluations will be based on the safety set.

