The choice of the MMRM model instead of a simple ANCOVA model on changes vs week 0 considering the prevalence approach or Last observation carried forward (LOCF) approach was done because the LOCF approach would underestimate the within-group mean changes between treatments compared with MMRM, whereas the prevalence approach tend to overestimate the within-group changes (Prakash et al. 2008).

In addition to that, similar MMRM model will be fitted on LOCF and prevalence set without the propensity score approach. An unstructured covariance matrix for the repeated measures within each patient will be applied in the analysis, if the model does not converge, compound symmetry will be used. The explanatory variables in the longitudinal model include cohort, visit, cohort-by-visit interaction, age, geographical region (i.e. north vs south vs central), BMI categories (<25 vs >=25), waist circumference, smoking status, metabolic syndrome (yes vs no), age at diagnosis of psoriasis, and along with interaction terms of each factor with visit.

The SAS codes are described in appendix section.

MMRM with MI approach

MMRM analysis will be also performed using multiple imputation (MI) approach on ITT population.

The multiple imputation will be done with pattern-mixture models (PMMs) as above, that allows formulating assumptions regarding missing data in a transparent and clinically interpretable manner.

The SAS codes are described in appendix section.

PASI 75

A logistic regression analysis model will be also fitted, considering age, geographical region, BMI, smoking status, metabolic syndrome, TNF α -308 polymorphism (if feasible), as well as all clinical relevant variable resulting statistically different at baseline between cohort, as strata factors. The analyses will be done similar to primary analyses based on prevalence, LOCF and NRI approaches using ITT set.

Time to reach PASI 90

The differences between cohorts Cw6-negative and Cw6-positive in time to reach PASI 90 will be evaluated by means of a log-rank test. The hazard ratios and their corresponding 95% confidence intervals will be also computed using a stratified Cox proportional hazards regression model with Cw6 group and baseline PASI as explanatory variable and stratified by geographical region and BMI categories, as well as age categories (tertiles).

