2.14 Interim analysis

No interim analysis is planned for this study.

3 Sample size calculation

The primary objective of this study is to evaluate the clinical response in PASI 90 at week 16 of Cw6-negative and Cw6-positive psoriatic patients. According to literature data, Cw6-positive patients will be about 60% of the entire psoriatic patient population.

From a previous study with ustekinumab (Talamonti et al. 2013) we can observe a difference in response to PASI 90 between Cw6-positive vs Cw6-negative patients of around 30%, in favor of Cw6-POS. Therefore, it is sensible to expect a response in the Cw6-negative cohort not less than 12 % respect to the Cw6-positive group. Further considerations are stated in the paragraph below.

Phase III data on secukinumab show a PASI 90 response at 16 weeks of 71%. Under the assumption that 60% of all the enrolled patient population is represented by Cw6-POS patients, we can reasonably assume to observe a proportion of patients with PASI 90 of 80% in the Cw6-POS cohort.

Under these assumptions, considering a one-side alpha level of 0.025 and a power of 80%, 365 patients (219 Cw6-POS and 146 Cw6-NEG) are sufficient to evaluate if the response in terms of PASI 90 in the Cw6-negative cohort is not less than 12% respect to the Cw6-positive cohort.

Considering a dropout rate at 16 weeks of 10% equally divided in the two studied cohorts, a total of 406 patients should be enrolled.

All calculations were done with NQuery 7.0.

A power analysis based on a different Cw6 patient distribution was made in order to facilitate patient enrollment without power-loss in the primary endpoint evaluation. Table 3-1 shows how the enrollment rate should be set free until the ratio between Cw6-POS and Cw6-NEG reaches the 1:1 rate-distribution, with a power of at least 80%.

In particular, the number of Cw6-POS evaluable patients will range from 219 to 182, whereas those in the Cw6-NEG cohort will range from 146 to 182.

Based on the table below, the enrollment in one of the two cohorts will be stopped when the target number is achieved (a maximum of 244 Cw6-POS patients will be allowed).

Table 3-1:Power analysis

Power	Ratio	Cw6	Cw6	Cw6	Cw6	Overall	Cw6	Cw6	

For business use only

		POS	POS	POS	POS		POS	POS
		%	%	Ν	Ν	Ν	%	%
80%	0.66	60%	40%	219	146	365	244	163
80%	0.70	59%	41%	215	150	365	239	167
80%	0.72	58%	42%	212	153	365	236	170
80%	0.75	57%	43%	209	156	365	233	174
81%	0.79	56%	44%	204	161	365	227	179

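### The week 36–72 response rates have two unreconciled denominators, entrants and ITT; patients who do not enter the extension have no stated rule, and time to response has no censoring definition

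*SAP*

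**What the plan says.** **Denominator.** For by-phase summaries, SAP 1.1 sets the extension denominator: "total number of patients (N) for extension phase will be the number of patients who have entered the extension". It adds: "All percentages in extension phase will be based on this N". SAP 2.1.1.5 then sorts data into phases for by-phase analyses. It introduces the visit data with "For Planned data (i.e., Visit wise, all safety and efficacy) will be derived as below" and assigns visits on or after E0 to the extension phase.

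**Analysis set.** SAP 2.2 states: "The primary and secondary objectives will be evaluated on the ITT population". In SAP Table 1.2-1 the primary endpoint runs on to week 72, and a secondary objective compares PASI 50/75/90/100 between cohorts at every time point.

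**Who leaves.** Protocol 5.5.9: "Patients that do not achieve PASI 50 at week 16 will terminate treatment". Protocol 4.3 admits to the extension patients judged to benefit "based on at least a PASI 75 response rate after 24 weeks of treatment", and patients must also be willing. Protocol Table 6-1 treats week 24 as the end-of-study visit for those who do not proceed. No later PASI is scheduled for them.

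**Missing data.** SAP 2.5.3 applies LOCF and NRI to drop-outs and to intermediate missing visits, and extends this to PASI 90 in the extension. Its one exemption is for patients who entered the extension and completed the study before week 72. Patients who never entered are not mentioned.

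**Time to response.** SAP 2.7.2 says cohort differences "in time to reach PASI 90 will be evaluated by means of a log-rank test", with Kaplan-Meier curves and a stratified Cox model. Time to PASI 75 is handled the same way. SAP 2.7.3 has censoring in its heading but covers only LOCF and multiple imputation of PASI. The sample code in SAP 5.4.3 uses a censor flag that is defined nowhere.

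**The concern.** One aim of the extension is to learn whether Cw6 status influences long-term response. If the entrants-only denominator is applied to efficacy, each cohort's week 36–72 rate excludes that cohort's own poor responders. The figure answers how well week-24 responders hold their response. It does not answer what proportion of treated patients are in response, which is the question an ITT objective running to week 72 poses.

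Because the two rules are not reconciled, two analysts could follow the same SAP and report different week-72 rates.

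Time to response raises a related problem. Patients stopped at week 16 or not admitted at week 24 leave because they are not responding. If they are censored on leaving, Kaplan-Meier assumes they would later reach PASI 90 as often as those who stay.

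**Working it through.** **1. The plan's own figure.** SAP section 3 assumes 80% PASI 90 in Cw6-positive patients; its numbers imply 80% in Cw6-negative patients too. The margin is 12 points, one-sided alpha 0.025, with 219 + 146 evaluable.
- SE = √(0.16/219 + 0.16/146) = 0.0427.
- Power = Φ(0.12/0.0427 − 1.96) = 80.2%.
- 365/0.9 = 405.6, so 406 enrolled.

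The sample size reproduces. It concerns week 16 only and is not touched by this point.

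**2. Overall rate.** Planned entrants are about 306 (SAP 1.1): 306/365 = 83.8% of evaluable and 306/406 = 75.4% of enrolled. Non-entrants among 365 are 365 − 306 = 59. Let q be the rate in entrants and s the rate in non-entrants (both assumed):

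rate = (306q + 59s)/365

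| q | s | Rate among 365 |
|---|---|---|
| 80% | 0% | 244.8/365 = 67.1% |
| 80% | 30% | 262.5/365 = 71.9% |
| 80% | 60% | 280.2/365 = 76.8% |
| 80% | 80% | 80.0% |

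On 406 enrolled with no response outside the extension, the rate is 244.8/406 = 60.3%.

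**3. Cohort difference.** The documents give no entry rates by cohort. Assume true all-patient rates of 70% (positive) and 58% (negative), non-entrants counted as non-responders, and overall entry held at 83.8%. The entrants-only rate is the all-patient rate divided by the entry fraction.

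| Entry, positive / negative | Entrants-only rates | Difference (true: 12 points) |
|---|---|---|
| 83.8% / 83.8% | 83.5% / 69.2% | 14.3 |
| 86.0% / 80.5% | 81.4% / 72.0% | 9.3 |
| 88.0% / 77.6% | 79.5% / 74.7% | 4.8 |
| 90.0% / 74.6% | 77.8% / 77.7% | 0.0 |
| 92.0% / 71.6% | 76.1% / 81.0% | −4.9 |

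The difference starts to shrink once positive entry exceeds negative entry by about 2.6 points (2.3 points if the true rates are 80% and 68%). With true rates equal at 70% and entry 86.0% / 80.5%, a spurious difference of −5.6 points appears.

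**4. Kaplan-Meier.** All inputs are assumed. First PASI 90 by week 16: 80% positive, 68% negative. Stopped at week 16: 3% and 7%. Of continuing non-responders, 40% respond by week 24; of the rest, 40% do not enter; 50% of those entering respond later.

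Leavers kept as never-responders:
- Positive: 0.80 + 0.17×0.4 + 0.17×0.6×0.6×0.5 = 89.9%.
- Negative: 0.68 + 0.25×0.4 + 0.25×0.6×0.6×0.5 = 82.5%.

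Leavers censored:
- Positive: 1 − 0.20×0.6×0.5 = 94.0%.
- Negative: 1 − 0.32×0.6×0.5 = 90.4%.

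The week-72 gap is 7.4 points against 3.6. At week 24 it is 8.8 (86.8% vs 78.0%) against 7.2 (88.0% vs 80.8%). Over the other inputs tried, censoring raises the week-72 estimate by about 2–7 points in positives and 3–13 in negatives. With identical cohorts the gap stays at 0.

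**5. Cox.** A second assumed set, as percentages of each cohort (positive / negative): PASI 90 by week 16, 80 / 68; stopped at week 16, 3 / 8; new responders by week 24, 5 / 5; not entering, 7 / 13; later responders, 2.5 / 3. Spreading the early events evenly over weeks 4–16 gives a hazard ratio of 1.37 with leavers kept at risk and 1.34 with leavers censored. By week 16, 80/87.5 = 91% and 68/76 = 89% of events have already occurred, so the hazard ratio hardly moves.

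**The case against.** The strongest reply is that the entrants-only rule is confined to by-phase summaries, whereas PASI responses are specified by visit on ITT. SAP 2.5.3 carries LOCF and NRI into the extension and exempts only certain entrants, so poor responders may already count as non-responders. Sustained response in continuing patients is also a stated aim, and entrants-only rates answer it.

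Much of this stands. A reader might infer that every week 36–72 result is entrants-only; the documents do not settle that. But SAP 2.1.1.5 names efficacy data in the phase rule. A patient who finishes week 24 and does not proceed has completed the core study, and is neither plainly a drop-out nor missing an intermediate visit. The conflict is real.

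Three other readings go too far:

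- **That the Cw6 comparison is compressed.** The sign depends on cohort entry rates that the documents do not give; with equal entry a 12-point gap widens to 14.3.
- **That 80% really means 60%.** That uses 406, which includes the 10% dropout allowance, and treats every non-entrant as a non-responder, although some may be responders who decline.
- **That the time-to-response analyses are biased.** This depends on the undefined censor flag. If LOCF PASI feeds these analyses, stopped patients remain at risk and the problem does not arise. Patients who stop treatment are also asked to return for core visits to week 24 (Protocol section 6).

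**Conclusion.** The point holds as an unreconciled conflict and two missing definitions, and it should be corrected before the 72-week results are reported.

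- **Rates.** Entrants-only percentages are valid for maintenance among week-24 responders. As rates in all treated patients they are too high unless non-entrants respond equally often. On the planned numbers the excess over the evaluable-patient rate is at most 80% against 67%, and about 3–8 points if non-entrants respond at 60–30%.
- **Cohort difference.** It can widen, shrink, vanish or reverse. It shrinks only if the lower-responding cohort enters clearly less often.
- **Time to response.** Censoring patients who left for insufficient response would be informative. The harm falls mainly on the late Kaplan-Meier curve and little on the hazard ratio.

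Only the 306, 365 and 406 come from the documents. The response rates at week 72, the cohort entry rates and the Kaplan-Meier inputs are assumptions. The week-16 hypothesis test and its sample size are unaffected.

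**What to change.** 1. **SAP 1.1, 2.5.3 and 2.7.2.** Make the week 36–72 cohort comparison of PASI 75/90/100 on the ITT N. Count patients stopped at week 16, or ineligible at week 24, for insufficient response as non-responders at later visits. State the imputation rule for responders who decline entry. Keep the existing exemption for entrants who complete before week 72. Report PASI 50 after week 24 among entrants only: a patient between PASI 50 and PASI 75 at week 24 is ineligible yet is a PASI 50 responder, so scoring that patient as a PASI 50 failure would be unjustified.
2. **Entrants-only table.** Keep it, labelled as maintenance among week-24 responders.
3. **Time to PASI 90/75.** Define the event time and the censoring time. Keep patients who left for insufficient response event-free in the risk set to week 72, and censor other patients at their last PASI assessment.

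The cost is SAP wording, one extra set of tables and lower reported 72-week rates. Non-entrants' late status would be imputed, since no PASI is scheduled for them after week 24. No treatment or eligibility rule changes.
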